7.6 Statistical Analysis

A detailed analysis plan will be developed and agreed by the Trial Steering Committee and the Data Monitoring Committee, prior to unblinding and data analysis.

Demographic factors and clinical characteristics will be summarised with counts (percentages) for categorical variables, mean (standard deviation[SD]) for normally distributed continuous variables, or median (interquartile [IQR] or entire range) for other continuous variables. Numbers of participants who are eligible, recruited, and followed up will be recorded in a CONSORT flow-chart.

Adjusted and unadjusted (crude) treatment effects will be estimated using multivariable and univariate regression analysis, respectively. Binary outcomes (peripartum transfusion, requirement for anti-D antibody and any other binary secondary outcomes) will be analysed with logistic regression. Quantitative outcomes where a symmetric, unimodal distribution is expected (number of units transfused, volume of blood transfused, serum haemoglobin, Multidimensional Fatigue Inventory) will be analysed with linear regression. Quantitative outcomes with strongly skewed distributions (maternal exposure to fetal blood, dose of anti-D antibody) will have cut-offs defined in the analysis plan and will be analysed as binary variables. Time-to-event outcomes (time to first mobilisation, length of hospital stay) will be analysed with Cox proportional hazards regression. The analysis of post-operative serum haemoglobin will allow for change from baseline by including the pre-operative level as an additional covariate. Differences between treatment effects in different subgroups (in planned subgroup analyses and in exploratory analyses) will be analysed with tests for interactions. $P < 0.05$ will be used to determine statistical significance in all analyses.

Analyses will be intention-to-treat; for this reason every effort will be made to collect complete data for all randomised participants. Where baseline covariates are missing we will use mean imputation of the covariate or a missing indicator covariate in adjusted analyses (note that epidemiological arguments against the use of a missing indicator do not apply in randomised trials) (27) An intention-to-treat approach does not mean that all outcome data must have been collected (28), though pilot work for this trial suggests that all or close to all of the primary outcome data will be obtained. Where outcome data are missing we will analyze those who do have outcome data, adjusting for baseline covariates. This approach is unbiased if missingness for the outcome is related to observed covariates

("missing at random"). Further sensitivity analyses will be used if necessary to explore the missing at random assumption.

The study statistician and chief investigator will remain blinded so as not to bias the analysis and interpretation of results. An independent statistician employed by the PCTU will provide the DMC statistician with the key to unblind the data, and the study statistician will provide computer code to allow the DMC statistician to produce unblinded summaries as required by the DMC.

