1.3 Rationale and Risks/Benefits

1.3.1 Risks

Previously the obstetric setting was a contraindication to the use of IOCS because of theoretical concerns regarding the risk of amniotic fluid embolus, a serious but extremely rare (about 1 in 20,000) complication of pregnancy/childbirth. As our understanding of this condition has improved, the theoretical risk has greatly reduced. Studies examining the quality of blood that would be returned to the mother, had IOCS been used at caesarean section, have shown that, with modern equipment, there is no difference between blood processed at caesarean section and returned to the mother and normal maternal blood (10;11).

Another potential risk associated with IOCS is “Rhesus sensitization”. Rhesus disease occurs when there is an incompatibility between antibodies carried on red blood cells of a woman and her infant e.g. a rhesus-negative (Rh-) woman giving birth to a baby with a rhesus-positive (Rh+) blood type. Contact between maternal and fetal blood may provoke an immune response in the maternal immune system. The antibodies produced can induce fetal haemolytic disease in future pregnancies. There is no evidence to suggest that IOCS increases the risk of sensitization.

Maternal exposure to fetal blood is measured using a Kleihauer test. All rhesus-negative women delivering by Caesarean section receive anti-D antibody injection to prevent sensitization. This risk is therefore not appreciably different between women in the IOCS or standard care groups. The National

Institute for Health and Clinical Excellence (NICE) has issued guidelines regarding the use of IOCS in obstetrics. They state that the technology may be of benefit with careful patient selection. In addition to NICE, IOCS in obstetrics is also recommended by CEMACH (Confidential Enquiry into Maternal and Child Health), the RCOG (Royal College of Obstetricians and Gynaecologists), the OAA (Obstetric Anaesthetists Association) and the AAGBI (Association of Anaesthetists of Great Britain and Ireland) in the UK and the ASA (American Society of Anesthesiologists) in the USA.

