5.2 Sample Collection/Labelling/Logging

Sample collection requirements include full blood count (FBC) for analysis of haemoglobin levels at both pre and post-operative time points. A Kleihauer test is also required to measure maternal exposure to fetal blood postoperatively. The requirement for anti-D will be determined by analysis of maternal and fetal blood types and rhesus status postoperatively. These tests are considered to be standard care for women undergoing caesarean section and do not constitute additional tests for trial purposes. Samples will be collected, labelled and processed according to NHS standard practice and logged onto the NHS database.

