7.1.3 Safety outcomes

- Pre- and post-operative serum haemoglobin, and mean fall in haemoglobin level
- Maternal exposure to fetal blood measured by Kleihauer test
- Requirement for and the dose of anti-D antibody administered

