7.4 Safety Endpoints

Adverse events will be recorded from the time of randomisation to the time of discharge. Safety outcomes will be compared between the groups, as for secondary endpoints.

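### Requirement for anti-D is set by blood groups fixed before randomisation, so the planned logistic regression of requirement by arm cannot show any effect of IOCS

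*Protocol*

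**What the plan says.** Protocol 7.1.3 lists among the safety outcomes "Requirement for and the dose of anti-D antibody administered". Section 7.4 adds: "Safety outcomes will be compared between the groups, as for secondary endpoints". Section 7.6 then names the method: "Binary outcomes (peripartum transfusion, requirement for anti-D antibody and any other binary secondary outcomes) will be analysed with logistic regression". The same section sets a threshold of 0.05 that "will be used to determine statistical significance in all analyses".

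Two other sections say what decides requirement. Section 5.2: "The requirement for anti-D will be determined by analysis of maternal and fetal blood types and rhesus status postoperatively". Section 1.3.1: "All rhesus-negative women delivering by Caesarean section receive anti-D antibody injection to prevent sensitization", followed by the inference "This risk is therefore not appreciably different between women in the IOCS or standard care groups".

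Section 7.6 also plans two related analyses. Anti-D dose and maternal exposure to fetal blood are each to be cut at a value set in the analysis plan and analysed as binary outcomes. For the analysis set it says "Analyses will be intention-to-treat; for this reason every effort will be made to collect complete data for all randomised participants". It states no restriction to rhesus-negative women.

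**The concern.** A between-arm safety test is useful only if the treatment could change the variable. Requirement for anti-D, as sections 5.2 and 1.3.1 describe it, depends on the mother's blood group, or on hers and the baby's. The laboratory reports these after the operation, but they are settled before allocation. Returning more fetal blood with the salvaged cells would not move any woman from not requiring anti-D to requiring it.

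Rhesus sensitisation is one of the potential risks of IOCS named in 1.3.1. A null result on requirement could be read as reassurance about it, and a significant one as harm or benefit. Neither reading would be justified. This does not wait on the analysis plan, because the protocol itself fixes both the outcome and the model; what it defers is the cut-offs for dose and fetal-blood exposure.

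**Working it through.** **Inputs from the protocol.** 1,525 women per arm (7.5); 1:1 allocation (4.3); two-sided 5% level; requirement defined as in 5.2 and 1.3.1.

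**The plan's own figure.** The protocol gives no figure for anti-D. Its primary sample size confirms the arm size and the type of formula. For 5% v 3%, 80% power and pooled variance under the null, n per arm = [1.96·√(2·0.04·0.96) + 0.8416·√(0.05·0.95 + 0.03·0.97)]² / 0.02² = (0.5432 + 0.2329)² / 0.0004 ≈ 1,506. The total is 3,012, as in the 5% row of the table in 7.5. Adding the 38 losses gives 3,050.

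**Step 1: the true effect on requirement.** If blood groups decide requirement, its probability f is the same in both arms under any effect of IOCS. The true odds ratio is 1. Simulated Wald tests of the log odds ratio with 1,525 per arm rejected in 4.9% to 5.0% of trials for f from 5% to 20%. The protocol gives no f, so that range is an assumption.

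**Step 2: how far chance alone moves the result.** The standard error of the difference is √(2f(1−f)/1525), and that of the log odds ratio is √(2/(1525·f(1−f))).

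| Assumed f | SE of difference (points) | 95% chance range of odds ratio |
|---|---|---|
| 5% | 0.79 | 0.72–1.38 |
| 10% | 1.09 | 0.79–1.27 |
| 15% | 1.29 | 0.82–1.22 |

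**Step 3: what the planned dose outcome can do.** Suppose the cut-off marks extra dosing, at rates p₁ and p₂ among women who need anti-D. Power = Φ[(|p₁−p₂| − 1.96·s₀)/s₁], where s₀ uses the pooled rate and s₁ the separate rates. In the subset, n = 1525f per arm. In all women, n = 1525 and the rates become f·p₁ and f·p₂.

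Worked example, f = 10%, 10% v 25%:
- Subset, n ≈ 152.5: s₀ = √(2·0.175·0.825/152.5) = 0.0435; s₁ = √((0.09 + 0.1875)/152.5) = 0.0427; (0.15 − 0.0853)/0.0427 = 1.52, power 93.5%.
- All women, 1% v 2.5%: s₀ = 0.00475; s₁ = 0.00474; (0.015 − 0.0093)/0.00474 = 1.20, power 88.5%.

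| Assumed f | Subset per arm | 10% v 25%: all women | 10% v 25%: subset | 10% v 15%: subset |
|---|---|---|---|---|
| 5% | about 76 | 60.4% | 68.7% | 15.2% |
| 10% | about 153 | 88.5% | 93.5% | 26.1% |
| 15% | about 229 | 97.3% | 98.9% | 36.5% |

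The extra-dose rates are assumptions too. Restricting to the subset adds about 8, 5 and 2 points at 10% v 25%. What matters is testing dose and not requirement.

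**The case against.** The best reply is that little is lost. The protocol already plans a dose-above-cut-off outcome and a direct Kleihauer measure, and both can respond to IOCS. That stands. A reader might infer that the trial has no working check on rhesus-related harm; the documents do not support this.

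A second reply concerns the analysis set. Nothing in 7.6 says explicitly that anti-D is analysed in all women. That is inferred from the intention-to-treat statement and the lack of a stated restriction, and the analysis plan may set a denominator. This stands as a caution, but it does not rescue requirement: among rhesus-negative women the baby's group is equally fixed before surgery.

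Third, requirement might have been meant to cover a need for more anti-D after the Kleihauer test. Section 5.2 mentions that test separately and ties requirement to blood types. If another meaning was intended, the definition has to change.

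Fourth, 1.3.1 already expects no appreciable difference in sensitisation risk between arms, so a null would add limited false reassurance, particularly beside the dose and Kleihauer results. That is fair and bears on the weight of the point. It also means that the protocol's own reasoning leaves this test nothing to find.

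**Conclusion.** The point holds for requirement only. On the protocol's text, its regression by arm has a true odds ratio of 1 under any effect of IOCS and a 5% chance of significance. A difference could reflect only chance, or differences in recording or administration.

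It would be too strong to conclude that the subset analysis turns an uninformative comparison into a well-powered one. The fair comparator is the dose analysis already planned, and against that the gain is modest. For smaller effects the subset is underpowered too. All power figures rest on assumed rates of requirement and extra dosing, and on the cut-off marking extra dosing.

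The conclusion about requirement needs no assumed rate. It rests on 5.2 and 1.3.1, and holds under either, although they differ on who is counted: mother's group alone, or mother's and baby's. The primary outcome and the sample size are unaffected.

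**What to change.** In 7.1.3 and 7.6, take requirement for anti-D out of the tested binary outcomes and report it descriptively by arm, as the denominator for the dose outcome.

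Base the anti-D comparison on the planned dose-above-cut-off outcome, analysed in women for whom anti-D is indicated by maternal and baby blood group. Report fetal-blood exposure in that subset as well. Allocation cannot affect membership of the subset, so the randomised comparison is preserved, provided membership is taken from blood group and not from whether anti-D was given.

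Reconcile 1.3.1 and 5.2 on who is counted as requiring anti-D. This concerns the outcome definition; no clinical rule is proposed.

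The cost is wording. The case report form in 8.3 already has an item for anti-D requirement and dose. The downsides are a smaller denominator and a dose cut-off that the analysis plan must still set. If that cut-off is to be relative to each site's usual amount, that amount must be obtained, since 8.3 does not list it.

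### Section 7.6 makes a binary split the only analysis of fetal-blood exposure because the measure is skewed; an analysis that keeps the Kleihauer values should be added beside it

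*Protocol*

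**What the plan says.** Section 7.1.3 of the protocol lists three safety items without ranking them: haemoglobin, "Maternal exposure to fetal blood measured by Kleihauer test", and "Requirement for and the dose of anti-D antibody administered". Section 7.4 has safety outcomes compared in the same way as secondary endpoints, and section 7.3 adjusts those for the primary-analysis covariates.

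Section 7.6 sets the method by type of outcome. Of the two variables that it calls strongly skewed, fetal-blood exposure and anti-D dose, it says that they "will have cut-offs defined in the analysis plan and will be analysed as binary variables". The cut-offs are left to an analysis plan "agreed by the Trial Steering Committee and the Data Monitoring Committee, prior to unblinding and data analysis". Requirement for anti-D is handled separately: "Binary outcomes (peripartum transfusion, requirement for anti-D antibody and any other binary secondary outcomes) will be analysed with logistic regression".

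Section 7.6 plans no analysis of either skewed variable that keeps the measured values, whether log-scale, rank-based or ordinal.

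**The concern.** The protocol itself settles the method and defers only the cut-off value, so this is not a detail left to the analysis plan. The reason stated is the shape of the distribution; no clinical threshold is mentioned. Skew argues against ordinary linear regression on the raw scale. It does not argue for reducing the measure to two categories, because ordinal regression copes with skew, ties and a mass at the lowest value, accepts the same covariates, and extends the logistic model already planned.

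Fetal-blood exposure bears on the sensitisation risk discussed in section 1.3.1, and section 6.4.1 lists it among the risks related to trial procedures. Section 7.6 judges every analysis at P<0.05. If exposure rises modestly across many women, a binary split makes that harder to see, and a non-significant safety comparison is easily read as reassurance.

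Anti-D dose raises a separate difficulty. A cut at zero repeats the requirement analysis, and a cut elsewhere merges non-recipients with lower-dose recipients. Either way, the dose information that section 7.1.3 asks for is largely unused.

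**Working it through.** **The plan's own figure.** The protocol gives no power or information figure for these outcomes. Its sample size (section 7.5) supplies the group size used below, so it was checked first. With 5% v 3%, two-sided 5%, 80% power and pooled variance:

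n = [1.960·√(2·0.04·0.96) + 0.842·√(0.05·0.95 + 0.03·0.97)]² / 0.02² = 1,506 per group, or 3,012 in total.

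Adding the 38 allowed losses gives 3,050. Power at 1,525 per group is 80.5%. The stated design reproduces.

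**Step 1: information lost by one cut, under a general shift.** Assume that exposure is normal on some transformed scale, such as the log, and that treatment shifts every woman equally. Let q be the share of women above the cut and z the matching normal quantile. Efficiency of the split relative to the full measure is φ(z)²/[q(1−q)]. A rank test has efficiency 3/π = 0.955 on the same basis, so the split relative to a rank test is the first figure divided by 0.955.

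| Women above the cut | φ(z)²/[q(1−q)] | Divided by 0.955 | Loss v rank test |
|---|---|---|---|
| 50% | 0.637 | 0.667 | 33.3% |
| 25% | 0.539 | 0.564 | 43.6% |
| 10% | 0.342 | 0.358 | 64.2% |
| 5% | 0.224 | 0.235 | 76.5% |
| 1% | 0.072 | 0.075 | 92.5% |

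Worked line for 10%: z = 1.2816, φ = 0.1755, φ² = 0.0308, and 0.0308/0.09 = 0.342.

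**Step 2: the same in power.** Assume a shift of 0.12 SD on the log scale and 1,525 women per group. For the full measure, 0.12·√(1525/2) − 1.96 = 1.35, giving 91% power. A median cut gives 75%. A cut with 25% above gives 69%, with 10% above 51%, and with 5% above 37%.

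**Step 3: many undetectable values.** The same shift was simulated with values below a detection floor tied (1,500 replicates per setting, Monte Carlo standard error at most about 1.3 percentage points).

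| Detectable share | Cut (share above) | Rank test power | Binary power |
|---|---|---|---|
| 50% | 50% | 85% | 76% |
| 25% | 25% | 72% | 70% |
| 10% | 10% | 53% | 52% |
| 25% | 10% | 73% | 53% |
| 10% | 5% | 53% | 38% |

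When most values are undetectable, a detectable/undetectable split loses almost nothing. A cut well above the floor still loses power.

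**Step 4: effect confined to a few women.** Assume 3% of one arm is shifted by 3 SD and the rest are unchanged. Power is about 65% for a t-test and 29% for a rank test. For the split it is 60% with 10% above the cut, 84% with 5%, 97% with 2%, and only 13% at the median. Here a tail cut is clearly the better test.

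**Step 5: anti-D.** Section 1.3.1 says: "All rhesus-negative women delivering by Caesarean section receive anti-D antibody injection to prevent sensitization". Section 5.2 has requirement determined from maternal and fetal blood types and rhesus status. Zeros therefore mainly mark blood type, which treatment cannot change. The shift model of step 1 does not describe such a variable, and its percentages are not applied to it.

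**The case against.** The best defence is that a cut may be the right tool for harm. If the worry is a small number of large exposures, step 4 shows a tail cut far outperforming a rank test, and a proportional-odds model is essentially the covariate-adjusted form of that rank test. Replacing the binary analysis could weaken the safety comparison. This stands, and it is why the binary analysis should stay as a reported analysis and not be reduced to a footnote.

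It is also fair that the cut-offs are to be agreed before unblinding. That is pre-specification and not a fault, and nothing prevents the analysis plan from choosing clinically based values.

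Three stronger readings are tempting, and the documents do not support them:

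- A reader might infer that the plan throws away a fixed share of the information, say a third to three quarters. The protocol gives no distribution, detectable share, cut-off or effect size. Steps 1, 3 and 4 show that the loss could exceed 90%, be near zero, or turn into a gain.
- A reader might take this for the trial's main safety question. Section 7.1.3 ranks no safety outcome. Section 1.3.1 discusses amniotic fluid embolus first and says of sensitisation: "There is no evidence to suggest that IOCS increases the risk of sensitization".
- A reader might extend the ordinal model to anti-D dose with zero as the lowest category. That would largely model rhesus status (step 5).

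The defence does not justify having only the binary analysis. The protocol does not say which pattern of effect it expects, and its stated reason is skew.

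**Conclusion.** The point holds as a modest one about efficiency on a listed safety outcome. Section 7.6 commits to a binary analysis alone for fetal-blood exposure, for a reason that does not require it. Under a uniform shift on a normalising scale, the loss against a rank-based analysis is about 33% at the median, 64% with 10% above the cut and 76.5% with 5%. The loss is near zero under a large undetectable floor with the cut at that floor, and a tail cut is superior when a few women have large exposures. Because the pattern is unknown at the planning stage, reporting both analyses covers each case. For anti-D, the defect is that a cut dose either repeats the requirement outcome or mixes non-recipients with recipients. Neither the primary analysis nor the sample size is touched.

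**What to change.** In section 7.6:

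- **Kleihauer result.** Keep the binary analysis at the cut-off pre-specified in the analysis plan. Add a pre-specified proportional-odds ordinal regression on the recorded values, with undetectable values as the lowest category, adjusted for the primary-analysis covariates. Report both, whatever each shows.
- **Anti-D.** Leave requirement as the binary outcome. Summarise or compare dose on its recorded values among recipients, and do not put dose and zeros in one model.

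No new data are needed: section 5.6 has the Kleihauer result transcribed to the CRF, and section 8.3 records anti-D requirement and dose there. The cost is a wording change and one extra safety analysis whose effect measure, a common odds ratio across categories, is less familiar. The binary result beside it eases interpretation.

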7.7 Health Economics Analysis

The aim of the economic evaluation is to determine the relative cost-effectiveness of the IOCS compared to current practice. The economic evaluation will be carried out from the perspective of the NHS therefore only direct costs and outcomes to the health service associated with the intervention will be included in the analysis and these direct costs will include those associated with adverse events. The evaluation will consider costs incurred by the health service in the delivery of the alternative treatment pathways and given the duration of follow up in the trial is for the immediate post natal period until discharge from hospital, it is a pragmatic decision to limit the perspective to the NHS. There is no reason to expect the alternative strategies to cause significant variation in the private costs to individuals, or to society, between the arms of the study beyond this time point, so wider costs such as primary data on the private out of pocket costs to individuals associated with the study will not be collected.

